Executive Function (EF) and Self-Neglect (SN): Individuals who SN often suffer from dementia, depression, and pain, all associated with ED. Additionally, SN is associated with impaired social networks and refusal of care. Prior research indicates that, when self-neglecters refuse interventions of unpaid caregivers, there is progressive decline in personal, functional and environmental domains. Secondary Aims have been added to further understand the relationship of ED with psychosocial outcomes and refusal of care. Although the APT intervention is primarily directed to the caregiver, participation of the PWD in weekly homework is critical. Better understanding the relationship of these variables will help to inform later analyses. The CLOX Drawing Test will be administered to a subset of 100 consecutively enrolled subjects at baseline. It is a two part test (CLOX 1 and CLOX 2) to measure EF and global cognition. CLOX 1 is a more direct measure of EF. CLOX 1 consists of instructing the subject to draw a clock and insert the time of 1:45 using hands and numbers in a clock. Scores range from 0 to 15. A score of 10 or below on CLOX 1 indicates executive impairment. The CLOX has high inter-rater reliability estimates (CLOX 1, Pearson, s r = 0.94, CLOX 2, Pearson, s r = 0.93; both p < 0.001). The CLOX also has a high internal consistency (Cronbach; s alpha = 0.82). After adjusting for age and education level, the Executive Interview and Mini-Mental Status Examination strongly predicted CLOX 1 scores [F (4,82) = 50.7, p < 0.001; R2 = 0.71]. Refusal of care will be measured by clinician assessment at each weekly session with the following two questions: ¿¿How many weeks did the PWD participate in weekly sessions with the therapist?¿, and ¿How many weeks did the PWD participate in assigned homework?; Responses to each question range from 0-7 and will be summed and divided by the total number of sessions the caregiver participated in to determine the PWD; s rate of engagement in the intervention.

Section D: Purpose and Objectives

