The APT Intervention. APT is designed to reduce incidence of aggressive behavior in PWD with pain and/or pain-related features, who are at increased risk of aggression. It targets several areas of patient life that are known causes of aggression: pain, mood problems such as depression; lack of engagement in pleasurable activities; and difficulty in PWD/caregiver communication that may interfere with recognition of pain and negatively influence relationship quality. The intervention focuses most heavily on improving identification and management of pain through caregiver education and skill training. It also uses behavioral activation to increase pleasant events, known to be an important part of managing and preventing pain and treating depression. Finally, by providing training to improve communication skills, we expect to improve the quality of the PWD/caregiver relationship, improve the caregiver; s ability to effectively engage the PWD in the intervention, and enhance the caregiver is ability to advocate to the clinical provider on behalf of the PWD. Caregivers will receive 6 to 8 sessions of weekly treatment *** (see Section S PAVeD caregiver workbook and clinician workbook attachements for more information). Sessions lasting up to 45 minutes will be conducted in the PWD's home by licensed providers with behavioral health expertise. APT consists of 4 ¿core¿ sessions covering identification and management of pain, improvement of PWD-caregiver communication skills, and behavioral activation through increased pleasant activity planning. Two to 3 elective sessions build on core skills in these 3 areas, chosen with the PWD and/or caregiver through an assessment of collaborative goal setting during the first session. The intervention will be primarily geared toward the caregiver; but each session also provides opportunities for optional PWD involvement, depending on his/her dementia severity and willingness. Sessions will include didactics, skill-building, discussion, and role-playing (see Section S PAVeD caregiver workbook and PAVeD clinician manual attachments). Participants will also be provided a copy of Pain Management for Older Adults: A Self-help Guide as an additional resource for optional reading on topics covered in the intervention. All physicians with enrolled participants in either arm will receive CME modules pertaining to assessing and treating pain in older adults; this will increase their sensitivity toward and knowledge about pain identification. The Exit Interview attached in section S will be administered to all caregivers enrolled in the intervention group as soon as possible after their last home session to gather feedback on the intervention.

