Secondary Hypotheses 3: PWD who screen positive for ED will report significantly higher rates of pain (Philadelphia Geriatric Pain Intensity Scale), caregiver-patient related problems (Mutuality Scale), depression (30-item Geriatric Depression Scale) and behavior problems (Revised Memory and Behavior Checklist). Differences between those with and without ED in 1) pain, 2) mutuality, 3) depression, and 4) behavior problems will be evaluated with a series of multiple

linear regression models. Four models will be conducted, one for each outcome, with ED as the primary predictor and gender and caregiver relationship as covariates.

Secondary Hypotheses 4: PWD who screen positive for ED will have significantly lower engagement in intervention than PWD who do not screen positive for ED. An additional linear regression model will be conducted to test for differences between those with and without ED in engagement (Aim 2).

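### The engagement score for Secondary Hypothesis 4 is capped below the eight sessions the plan allows, and is labelled refusal of care although it also reflects non-involvement

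*Combined protocol and SAP*

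**What the plan says.** **The score.** Section C (Executive Function and Self-Neglect) states: "Refusal of care will be measured by clinician assessment at each weekly session with the following two questions". The questions are "How many weeks did the PWD participate in weekly sessions with the therapist" and "How many weeks did the PWD participate in assigned homework". Scoring follows: "Responses to each question range from 0-7 and will be summed and divided by the total number of sessions the caregiver participated in". The result is described as the PWD's rate of engagement. The same paragraph calls the PWD's part in the homework critical.

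**The sessions.** Section F2 (The APT Intervention) says "Caregivers will receive 6 to 8 sessions of weekly treatment". Section D gives the same range, and Section K allows as many as eight intervention visits per patient. F2 also describes four core sessions and adds "Two to 3 elective sessions build on core skills in these 3 areas"; Section D gives the same numbers of core modules and electives.

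**PWD involvement.** F2 says the intervention is aimed mainly at the caregiver and that "each session also provides opportunities for optional PWD involvement, depending on his/her dementia severity and willingness".

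**The test.** Section G, Secondary Hypothesis 4, reads: "PWD who screen positive for ED will have significantly lower engagement in intervention than PWD who do not screen positive for ED". It is tested by one linear regression. No covariate for dementia severity or number of sessions is named for it.

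**The concern.** Two things do not fit together.

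First, an item that cannot exceed 7 is divided by a session count that can reach 8. Two PWD with the same complete participation can then receive different scores only because their courses differed in length. The question wording adds a second uncertainty. It asks for a count of weeks at every weekly session and does not say whether the last answer or all the answers enter the sum, so two analysts could build different outcomes from the same forms.

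Second, the label claims more than the items record. A PWD who stays out of a session because of severity and a PWD who declines it get the same score. If ED goes with greater severity, an ED-positive group could score lower with no difference in willingness. At stake is the interpretation of Hypothesis 4: a positive result might be reported as ED leading to refusal of care when it shows only lower participation.

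**Working it through.** **1. The plan's own figure.** The documents give no numerical value for the score. The nearest stated figure is the power of the ED regressions in G1: N = 100, alpha 0.05, ED tested over two covariates. With a noncentral F on 1 and 100 − 3 − 1 = 96 degrees of freedom and λ = f² × N:

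- f² = 0.15: λ = 15, power 96.95% (stated 97%).
- f² = 0.08: λ = 8, power 79.96% (stated 80%).

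Both reproduce. The scale of the outcome does not enter this calculation, so it does not bear on the point.

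**2. Score at full participation, plain reading.** Inputs: item cap 7 (Section C); S = 6, 7 or 8 caregiver sessions (D, F2, K). The final count is used for each item. A PWD who joins every session and does every week's homework scores 2 × min(S, 7) / S.

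| S | Calculation | Score | Divided by 2 (0-to-1 scale) |
|---|---|---|---|
| 6 | (6 + 6)/6 | 2.00 | 1.00 |
| 7 | (7 + 7)/7 | 2.00 | 1.00 |
| 8 | (7 + 7)/8 | 1.75 | 0.875 |

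The loss at eight sessions is (2.00 − 1.75)/2.00 = 12.5%. Six and seven sessions score the same. Four core plus two or three electives is 4 + 2 = 6 or 4 + 3 = 7, so under that description the cap never binds.

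**3. Variant: homework possible only from the second session on.** Full participation scores (6 + 5)/6 = 1.83, (7 + 6)/7 = 1.86 and (7 + 7)/8 = 1.75. Here six and seven also differ slightly, and eight remains lowest.

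**4. Effect of the cap on the group comparison.** Only a count of 8 is clipped, by 1 on that item, which costs 1/8 = 0.125; clipping on both items costs 0.25. The cap can therefore shift the ED-positive versus ED-negative mean difference by at most 0.25 × (difference between groups in the share with full participation over eight sessions). That lies between 0 (equal shares) and 0.25 (all against none), in either direction. The documents do not give the shares.

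**5. Mixing of reasons.** Take two PWD with six sessions each and homework done every week. One is left out of three sessions because of severity; the other declines three. Both score (3 + 6)/6 = 1.50. The two items as worded cannot tell them apart.

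**6. Link between ED and severity.** Section C reports that the Executive Interview and the Mini-Mental examination strongly predicted CLOX 1, with R² = 0.71 after allowing for age and education. That R² belongs to the whole model. It makes a link with general cognition plausible but gives no figure for ED and severity in this trial.

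**The case against.** The strongest reply is that Hypothesis 4, and the objective in Section D, concern engagement, and taking part is engagement whatever the reason. The refusal label occurs in the background section. This largely stands: the score is a usable basis for participation, and the label is what needs to change.

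The 0-7 range also fits a six- or seven-session course exactly. That stands too, but three sections allow eight, so the mismatch is real until the counts are reconciled. A maximum of 2 instead of 1 does no harm in a linear regression.

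A reader might infer more than the documents support:

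- **That the score cannot measure refusal at all.** F2 names willingness alongside severity, optional describes session involvement only, and homework, half the score, is called critical. The score is a mixed proxy that carries some information on refusal.
- **That scores diverge across the whole range of session counts, by up to 25%.** Adding the running counts from every session gives 7.0, 8.0 and 8.75 at six, seven and eight sessions. The text does not exclude this, but summing the two items is the more natural sense, so these figures show the ambiguity and not the size of the error.
- **That 0-7 means days per week.** Both questions ask for weeks.
- **That the predicted ED result would be an artefact.** Severity-related exclusion is possible, but enrolment is limited to mild-to-moderate dementia and its frequency is unknown. The session forms are attachments not available here, so it cannot be said that reasons go unrecorded everywhere.

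**Conclusion.** The concern holds as a fault of scaling and labelling. Applied as written, the rule gives full participation 2.00 at six or seven sessions and 1.75 at eight, a 12.5% loss from session count alone. This assumes that the final count is used and that homework can be done for every session. The resulting shift in the group comparison cannot exceed 0.25 on this scale, and its direction is unknown.

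Separately, a lower score with ED cannot be read as more refusal of care, because session involvement depends on severity as well as willingness. Any tilt toward the hypothesised result rests on the assumption that ED tracks severity. Its size cannot be computed from the documents.

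The point affects one secondary hypothesis in the CLOX subset and leaves the primary comparison untouched. It merits correction before Hypothesis 4 is analysed, because the rule is explicit and the repair is cheap.

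**What to change.** 1. At each session, record yes/no whether the PWD took part in the session and whether the PWD did the homework.
2. Define two outcomes, each from 0 to 1 with no cap at 7: sessions joined divided by sessions held, and homework assignments done divided by those assigned. This also removes the doubt about final versus weekly answers.
3. Reconcile the six-to-seven and six-to-eight session counts in Sections D, F2 and K.
4. Call the outcome participation or engagement, not refusal of care.
5. Add a sensitivity analysis of Hypothesis 4 adjusted for the severity measures already taken at screening (FAST and MIS-T). It addresses confounding by severity but does not separate refusal from non-involvement.
6. Optionally, record the reason for non-participation (not invited, unable, declined) and report it descriptively by ED status. Sessions with an invitation should not become the denominator: the decision to invite is likely to be related to impairment, and the ratio is undefined for a PWD never invited.

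The cost is a small change to a form completed at each session and a little extra analysis. Sessions already held will lack the reason for non-participation.

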Does this protocol/trial require registration on ClinicalTrials.gov due to it: meeting the definition of an Applicable Clinical Trial, being required under the terms and conditions of an award, or being proposed to be published in ICMJE journals?

No, this clinical is not a clinical trial, or does not meet the definition of an Applicable Clinical Trial, or does not need to be registered under the terms and conditions of an award, or is not a clinical trial with results intended to be reported in an journal belonging to the ICMJE. Registration is not required.

Section B: Exempt Request

B. Exempt From IRB Review

Not Applicable

Section C: Background Information

Optimal care and outcomes for persons with dementia (PWD) depend on family caregivers primarily responsible for care coordination and daily care. Behavioral or psychological disturbances are exhibited by 80% of PWD, including 40% who are aggressive. Growing evidence has addressed psychological disturbances of PWD and their caregivers once behavioral problems arise, but examination of prevention of such problems is lacking. Aggressive behaviors are perhaps the most problematic because they lead to increased institutionalization, injuries, caregiver burden and use of antipsychotic medications. Innovative approaches are urgently needed to replace the treatment of aggression with tranquilizing medications because of their associated morbidity and mortality in PWD. We have developed an innovative, behavioral caregiver intervention that aims to prevent development of aggression in at-risk PWD, guided by empirical evidence regarding mutable risk factors for aggression. Our team¿s prior work has identified patient pain and depression, and caregiver/PWD relationship quality as strong predictors of aggression.

Broadening Aggression Prevention Training (APT) to Be More Representative of Target Populations: The veteran sample in our current project is significantly different from the non-VA-using population in several important ways that compel us to test the intervention outside the VA. Almost all (97%) of our currently recruited dyads (n=130) are male Veterans with dementia, with women comprising 95% of the caregiver sample. Our sample is comparable to those of previous studies,

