z.r) Randomized, Efficacy Study -- Surgical Techniques/Interventions

Discuss the research design including but not limited to such issues as: probability of group assignment, potential for subject to be randomized to placebo group, use of control subjects, etc.

50% of patients will be randomized into the EU-PC and 50% into the APT intervention. It is equally likely that a participant will be randomized into either intervention. The RA will not know when consenting the subject if they will be in the active APT intervention or in the control group (EU-PC).

Inclusion Criteria:

Patients can participate in the study if they meet the following criteria: (1) have a documented diagnosis of dementia; (2) receive care from, BCM GMA, the BCM Alzheimer Center, or Kelsey-Seybold; (3) reside outside Nursing Home; (4) live within 40 miles of the Texas Medical Center; (5) have mild-to-moderate dementia; (6) have no history of aggression in the past month; (7) have an informal caregiver directly involved with them at least 8 hours a week who sees them at least twice a week; (8) speak English; and (9) report clinically significant pain, depression, or caregiver/PWD relationship difficulties (either self-report or caregiver proxy-report).

Exclusion Criteria:

Patients with advanced dementia will be excluded by 2 criteria: a) score of greater than 6 on the Functional Assessment Staging (FAST) scale; or b) inability to complete by phone the Memory Impairment Screen--Telephone Version (MIS-T) or Philadelphia Geriatric Pain Intensity Scale. PWD will also be excluded if they have been aggressive in the past month; we will administer the aggression subscale of the Cohen-Mansfield Agitation Inventory (CMAI).

F2. Procedure

Our patient identification and recruitment procedures are based on our prior studies of PWD. The key initial criterion for study eligibility for patients is having a dementia diagnosis. The research team will partner with participating sites through 3 recruitment mechanisms to identify PWD: (1) direct provider referral (2) patient self-referral and (3) partial HIPAA-waiver-approved, database-generated lists of patients meeting geographical and selected ICD-9 codes from the 046, 290, 291, 292, 294, 331 and 333 series (or corresponding ICD-10 codes).

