PWD identified through direct or database methods will receive a letter from the research team written at 6th-grade reading level to inform the PWD and caregiver that study staff will contact them the following week, unless they request not to be contacted by calling a toll-free number. PWD and caregivers will also be sent a Pain Thermometer as well as the response choices for the other study assessments/scales. A telephone script will be used to obtain verbal consent to administer the initial protocol screening, which will assess the presence of an eligible caregiver; clinically significant pain, depression or PWD/caregiver relationship difficulties; dementia of mild-moderate severity; absence of aggression; and willingness of PWD and caregiver to participate. Participant written informed consent for eligible and willing PWD and caregivers will be obtained in person or by mail immediately after the initial telephone screening appointment. A trained research assistant (RA) will administer the 15-minute telephone screen and informed consent to the caregiver and PWD. Following assent, caregivers will be asked a series of questions to assess level of PWD cognitive and functional impairment (FAST caregiver interview); presence of an eligible caregiver; and history of aggression, clinically significant pain or pain-related features, such as depression or caregiver/patient relationship problems. Prior to the RA¿s initiating the telephone screen, he/she will briefly describe the study and its voluntary nature to caregivers and PWD and obtain caregiver and patient verbal assent. PWD will be asked to complete the Mental Impairment Screen, telephone version (MIS-T) to collect further data regarding cognitive impairment and will also answer questions about their current level of pain, depression, and relationship with caregiver. PWD will be included if they screen positive for either: a) pain, b) depression, or c) caregiver/PWD relationship problems. We will screen for perceptions of pain using 2 measurement strategies. We will assess caregiver perceptions of the PWD¿s clinically significant pain with a screening question we have used previously: ¿During the past 4 weeks, did your [loved one/care recipient] often have physical pain, body aches, and/or discomfort?;, The PWDs;, perceptions of their own pain will be measured using 2 questions from the Philadelphia Geriatric Pain Intensity Scale, which assess pain intensity at time of assessment and over the past week. Both items use a response scale of 0 (no pain) to 5 (unbearable pain), presented as a thermometer graphic with verbal descriptors arranged

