In our prior and currently funded grants, we recruit patients using methods similar to those described in this proposal to identify PWD with clinically significant pain. To determine the number of patients available for this study, we asked our clinical partners to provide the number of PWD, using dementia ICD-IX codes and restricting to patients within 40 miles not living in a long-term care facility. We identified 1273 patients. Based on our prior studies, an estimated 60% of patients will meet the criterion for clinically significant pain, resulting in 764 existing eligible patients; broadening inclusion criteria to include pain-related features will result in even more eligible patients. On the basis of our prior recruitment data, we predict excluding approximately 30% of patients due to severe dementia, history of aggression, or lack of eligible caregiver. Thus, we estimate that 535 will meet all selection criteria. In our current APT study, we have had a consent rate of 80-90%. To conservatively estimate, an 80% consent rate results in 428 patients.

One-hundred consecutively enrolled subjects will be asked to do the CLOX Drawing Test at baseline to achieve our secondary objectives. This will give adequate power to detect significant differences of small to medium magnitude in outcomes between those with and without executive function (ED). Given an N of 100 and an alpha of 0.05, there is 97% power to detect a medium effect (F2 = 0.15) and 80% power to detect an effect size for ED (over and above two covariates) as small as F2 = 0.08.

Expected Recruitment Efforts and Minimization of Attrition. In our current VA Study and prior studies, we were able to enroll 6-8 dyads per month. In the VA study and others that we completed with PWD and their caregivers, attrition is about 10%; therefore, we plan to recruit 220 dyads, 6 patients per month over 37 months. We expect we will need to contact approximately 300 dyads using our partial HIPPA Waiver in order to enroll 220 dyads in the study.

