In general, the primary source of missing data will be through participant attrition. We anticipate a low attrition rate (10%) based on our prior work. As described below, we will use analytic techniques (eg, hierarchical linear models) that are robust to violation of missing-data assumptions (ie, ¿missing completely at random¿). To reduce the possibility of bias in missing data, where possible, we will incorporate information from secondary sources for participants with missing data from attrition to try to ascertain whether they differ in important ways from other study participants. We will use X2 tests to determine whether there are differences in attrition between the 2 study arms. Prior to testing hypotheses, we will compare baseline demographic and clinical variables in APT and EU-PC with X2 and independent sample t-tests. Variables with p values < .25 in these univariate tests will be included as covariates in all subsequent multivariate models107 or as propensity scores.

Primary Hypothesis: APT will result in lower 1-year incidence of aggression than EU-PC. We will use negative binomial regression models to estimate the difference between our intervention and the control group in the rate of aggressive behavior at the 1-year follow-up period. For participants who drop out of the study, their time until study attrition will be used as their exposure period. Statistical significance will be determined using the X2 statistic associated with the parameter estimate for group membership. Baseline demographic and clinical variables that differ between groups in univariate tests will be included as covariates or propensity scores.

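### The entry rule excludes only the past month's aggression, so recurrences can count toward the primary outcome, although the stated aim is to prevent aggression from developing

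*Combined protocol and SAP*

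**What the plan says.** **Entry.** Inclusion criterion 6 in Section F1 reads "6) have no history of aggression in the past month". The exclusion paragraph matches it: "PWD will also be excluded if they have been aggressive in the past month", assessed with the aggression subscale of the Cohen-Mansfield Agitation Inventory (CMAI).

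**Screening and recruitment text.** Section F2 lists what caregivers are asked at the telephone screen, including "history of aggression, clinically significant pain or pain-related features, such as depression or caregiver/patient relationship problems". Section J1a repeats this. Neither place gives a time window. The recruitment estimate in G1 is also unwindowed: "we predict excluding approximately 30% of patients due to severe dementia, history of aggression, or lack of eligible caregiver".

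**Aim and outcome.** Section C says the intervention "aims to prevent development of aggression in at-risk PWD". The primary hypothesis in the data analysis plan is that "APT will result in lower 1-year incidence of aggression than EU-PC". It is tested by negative binomial regression of the difference between arms "in the rate of aggressive behavior at the 1-year follow-up period". The text on nursing-home admission under Secondary Hypotheses 1 then refers back to the Hypothesis 1 analysis as a test of onset.

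**Covariates.** Under Attrition Rates and Missing Data, baseline variables enter the models if they differ between arms at p < .25. The Primary Hypothesis paragraph follows the same principle. Earlier aggression is not named as a covariate, stratum or subgroup.

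**The concern.** Development and onset point to first occurrence. The entry rule secures something weaker, namely that no aggression was recorded in the last month. Aggression that comes and goes can pass such a screen in a quiet spell and return during follow-up. The primary outcome can therefore mix first-ever aggression with recurrence, and the plan neither defines an incident case nor says how to tell the two apart.

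The main consequence is for what a positive result means. Preventing aggression in people who have never shown it is one claim. Reducing its return in people who have shown it is another. A single overall rate ratio cannot say which was achieved.

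There is a smaller consequence for precision. If earlier aggression predicts later aggression, leaving it out of the model adds variation between persons. Under the plan's covariate rule it would enter only if it happened to be imbalanced between the arms.

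**Working it through.** The plan gives no event rate, effect size or power for the primary outcome, and no figure for earlier aggression among those enrolled. There is thus no stated figure to reproduce. The check is first of wording, then of illustrative size.

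**1. Does the rule admit earlier aggression?** Take a PWD who was aggressive six months ago and not in the past month. Criterion 6 is met and the matching exclusion does not apply. The unwindowed references to aggression history in F2, J1a and G1 state no longer exclusion, so the one-month rule in F1 is the operative one. The PWD is eligible on this criterion.

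**2. Would a recurrence count?** The analysis is of the rate of aggressive behaviour over the year. No text restricts it to first-ever episodes, so a recurrence counts.

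**3. Could intermittent aggression pass the screen?** Assume episodes arrive as a Poisson process at L per month. Then P(pass) = exp(−L) and P(at least one episode in 12 months) = 1 − exp(−12L).

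| L (assumed) | P(pass one-month screen) | P(episode in 12 months) |
|---|---|---|
| 0.1 | 0.90 | 0.70 |
| 0.25 | 0.78 | 0.95 |
| 0.5 | 0.61 | 0.998 |
| 1 | 0.37 | >0.999 |

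**4. What share of PWD with aggression on study would be recurrent?** Let h be the share of the source population with such a history, and r the 12-month first-onset risk in the rest. Both are assumed.

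- Enrolled share with history: s = h·exp(−L) / [h·exp(−L) + 1 − h]
- Recurrent share: s(1 − exp(−12L)) / [s(1 − exp(−12L)) + (1 − s)r]
- Lowest case (h = 0.1, L = 1, r = 0.4): s = 0.039; share = 0.039 / (0.039 + 0.961 × 0.4) = 0.09
- Highest case (h = 0.4, L = 0.25, r = 0.2): s = 0.342; share = 0.325 / (0.325 + 0.658 × 0.2) = 0.71

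Over h = 0.1 to 0.4, L = 0.1 to 1 and r = 0.2 to 0.4, s runs from about 4% to 38% and the recurrent share from about 9% to 71%.

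A simpler form takes p as the enrolled share with earlier aggression and RR as their relative risk, both assumed: share = RR·p / (RR·p + 1 − p).

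| p | RR 2 | RR 3 | RR 4 |
|---|---|---|---|
| 0.1 | 0.18 | 0.25 | 0.31 |
| 0.2 | 0.33 | 0.43 | 0.50 |
| 0.4 | 0.57 | 0.67 | 0.73 |

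These are shares of persons, whereas the primary analysis is of a rate. They show only that the share need not be negligible.

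**5. Precision.** Read RR as a ratio of episode rates. The mixture then has squared coefficient of variation p(1 − p)(RR − 1)² / [1 + p(RR − 1)]². At p = 0.2 this is 0.16/1.44 = 0.11 for RR 2, and 1.44/2.56 = 0.56 for RR 4. It adds to the negative binomial dispersion and widens the interval for the arm effect. A covariate would recover some of it.

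**The case against.** The strongest reply is that incidence may simply mean new episodes after an aggression-free month in PWD at risk. That is a coherent target and fits the objective in Section D. It stands as a legitimate estimand, but the plan does not state it, and the language of development and onset points elsewhere.

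A second reply also has force. A reader might infer that onset and recurrence can never be separated afterwards. The documents do not support that. Caregivers are asked about aggression history with no stated window, F2 keeps screening answers as research data, and Section K lists progress notes among the health-record information (though not psychiatry notes). The telephone script is in Section S, which is not available here, so the reach of its question is unknown.

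A reader might also infer that earlier aggression is the strongest predictor of the outcome. No text says so; Section C names pain, depression and relationship quality as strong predictors.

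Finally, collecting the history late could do harm. The 8/18/17 amendment adds only 10 subjects, which suggests that most dyads were already randomised. Their caregivers know their arm, and APT trains them to understand the PWD's behaviour differently, so recall could differ by arm. That stands, and it limits the remedy.

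**Conclusion.** The concern holds as one of interpretation, with some loss of precision. The entry rule admits PWD with aggression before the past month, their recurrences count, and the plan does not distinguish them while describing its aim as preventing development.

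It is not a bias in the arm comparison: randomisation balances earlier aggression on average, and the negative binomial model allows for overdispersion.

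A reader might take the upper figures above to mean that much of any observed effect is control of relapse. The documents do not support that, because every input is assumed. The 40% aggression figure in Section C describes PWD in general, not mild-to-moderate PWD who passed an aggression screen. The roughly 30% in G1 combines three exclusion reasons and does not measure earlier aggression among those enrolled. The share of recurrences could be small or large. The precision argument likewise rests on the assumption that earlier aggression predicts later aggression.

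**What to change.** Leave eligibility unchanged.

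1. State the window of the screening question on aggression history (F2, J1a) and reconcile it, and the G1 wording, with the one-month rule in F1.
2. If that question does not reach back further, add one yes/no item at screening or baseline, before randomisation: did any behaviour on the CMAI aggression subscale occur before the past month?
3. Pre-specify the answer as a fixed covariate in the primary negative binomial model, whatever the p < .25 imbalance screen shows. Use only answers or records dated before randomisation. Answers collected afterwards belong only in a sensitivity analysis.
4. Describe the primary result as new aggression after an aggression-free month. Report rate ratios for PWD with and without earlier aggression descriptively. Do not claim prevention of first onset from the overall estimate, and do not move the main claim to the never-aggressive subgroup, for which no power is stated.

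The cost is at most one item on an existing call and a few lines of analysis text. The downsides are reliance on caregiver recall, incomplete pre-randomisation data for dyads already enrolled if the existing question proves too short, and imprecise subgroup estimates with 220 to 230 dyads.
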